2.2 Secondary objectives

Secondary Objectives:	Outcome Measures:
To examine the intra-patient variability of the change in 24-hour mean weighted glucose at the beginning and the end of the dosing cycle (Week 10 of treatment in EQW patients), using data obtained by a CGM system	Change in 24-hour mean weighted glucose between Day 1 of Week 10 (Day 64/65) and Day 6 of Week 10 (Day 69/70) within each EQW-treated patient
To compare the effect on fasting plasma glucose (FPG) and 2-hour PPG after 4 and 10 weeks of dosing of EQW plus metformin with placebo plus metformin	Change from baseline (Day 1) to Day 6 of Week 10 (Day 70) and Day 6 of Week 4 (Day 28) in FPG Change from baseline (Day -1) to Day 6 of Week 10 (Day 69) and Day 6 of Week 4 (Day 27) in 2-hour mean weighted PPG (after the breakfast meal)
To compare the following parameters after 4 and 10 weeks of dosing between the EQW plus metformin and placebo plus metformin treatment groups, using data obtained by a CGM system: the effect on 24-hour mean amplitude of glucose excursion (MAGE) the proportion of time patients who had plasma glucose measurements of: <70 mg/dL ≥70 mg/dL and ≤180 mg/dL or >180 mg/dL	Average of change in 24-hour mean weighted glucose from baseline (Day -1/1) to Days 1 to 6 of Week 10 and Week 4 calculated. (standard deviation [SD], MAGE, “Distance travel”, “Energy”)
To compare the effect on HbA1c levels and 2-hour PPG after 4 and 10 weeks of dosing of EQW plus metformin with placebo plus metformin	Change from baseline (Day -1) to Day 6 of Week 10 (Day 69) and Day 6 of Week 4 (Day 27) in 2-hour mean weighted PPG (after the breakfast meal)

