5.1.2.4 HbA1c

Assessment of HbA1c will be measured using the central laboratory measurement of HbA1c at Screening, Randomization (Day 1), Day 15, Day 22, Day 57, Day 64, Day 70, and ET.

5.1.2.5 MAGE, and the proportion of time patients who had plasma glucose measurements <70 mg/dL, ≥70 mg/dL, and ≤180 mg/dL, and >180 mg/dL

Mean amplitude of glucose excursion, and the proportion of time patients who had plasma glucose measurements <70 mg/dL, ≥70 mg/dL, and ≤180 mg/dL, and >180 mg/dL will be measured using the CGM system device. Mean amplitude of glucose excursion is calculated for each patient by taking the arithmetic mean of blood glucose increases or decreases (from blood glucose nadirs to peaks or vice versa) when both ascending and descending segments exceed the value of 1 SD of the blood glucose concentration in a 24 hour period.

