8.4.3 Exploratory endpoints

The exploratory endpoints for this study are the following:

- Change from baseline (Day -1/1) to Week 10 (Day 69/70) and Week 4 (Day 27/28) in the 24-hour MAGE using CGM system
- Change from baseline (Day -1/1) to Week 10 (Day 69/70) and Week 4 (Day 27/28) using CGM system, in the proportion of time patients who had plasma glucose measurements <70 mg/dL
- Change from baseline (Day -1/1) to Week 10 (Day 69/70) and Week 4 (Day 27/28) using CGM system, in the proportion of time patients who had plasma glucose measurements ≥ 70 mg/dL and ≤ 180 mg/dL
- Change from baseline (Day -1/1) to Week 10 (Day 69/70) and Week 4 (Day 27/28) using CGM system in the proportion of time patients who had plasma glucose measurements >180 mg/dL
- Change from baseline (Day 1) to Week 10 (Day 70) and Week 4 (Day 28) in HbA1c

- Change from baseline (Day -1) to Day 6 of Week 10 (Day 69) and Day 6 of Week 4 (Day 27) in 2-hour PPG (after the breakfast meal)
- Differences between mean daily 24-hour glucose profile during 7-day CGM system assessments during the lead-in period and 7-day CGM system assessments during Week 10.
 - Additionally, the relationship between exenatide exposure (steady-state concentration) and glycemic response (weighted average AUC_{0-24}) on Day 64 and Day 69 of the Week 10 steady-state dosing interval will be explored (SD, MAGE, “Distance travel”, “Energy”)

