8.5.1 Analysis of the primary variable(s)

The primary endpoint of 24-hour mean weighted glucose will be obtained by a CGM method and calculated as the AUC from the 24-hour glucose profile, divided by 24 hours. Details on AUC computations for partially missing 24-hour glucose profiles will be described in the SAP. The changes in 24-hour mean weighted glucose from baseline (Day -1/1) to Day 5-6 of Week 10 (Day 69/70) and to Day 6 of Week 4 (Day 27/28) will be analyzed using a maximum likelihood-based mixed model repeated measures (MMRM) method. The MMRM model will include change in 24-hour mean weighted glucose as the dependent variable; treatment, HbA1c stratum ($<8.5\%$ vs. $\geq 8.5\%$), baseline 24-hour mean weighted glucose, week of visit, and treatment-by-week interaction as fixed effects, and patient and error as random effects. All post-baseline measurements (including early termination visits) of the 24-hour mean weighted glucose will be included in the analysis with no imputation of missing data other than that inherent in the MMRM model. An unstructured covariance matrix will be used for the MMRM analysis, unless the model does not converge, in which case the covariance matrix will be decided upon model convergence status and the Akaike information criterion. The least squares (LS) means, standard errors of LS means, and 2-sided 95% confidence intervals (CI) for the mean change within each treatment group and the difference between treatment groups will be presented. P-values will be provided for the comparison between treatment groups. Data normality will be evaluated. If the data require logarithm transformation to meet the normality assumption for statistical modeling, the LS mean and the corresponding 95% CI will be calculated at the log scale, and the geometric mean ratio and its corresponding 95% CI will be calculated by taking the anti-log of the corresponding values within each treatment group and for treatment comparisons. The 2 primary endpoints will be tested sequentially (Week 10 comparison will follow by the Week 4 comparison) and the family-wise Type I error will be controlled between primary and secondary endpoints. See description in Section 8.5.2.

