8.5.2 Analysis of the secondary variable(s)

Intra-patient difference and variability of the 24-hour weighted mean glucose between Day 1 and Day 6 of Week 10 will be calculated and presented descriptively; no hypothesis testing will be performed.

The change in FPG from baseline (Day 1) to Day 6 of Week 10 (Day 70) and Day 6 of Week 4 (Day 28), and the change in 2-hour mean weighted PPG (after the breakfast meal) from baseline (Day -1) to Day 6 of Week 10 (Day 69) and Day 6 of Week 4 (Day 27) will be analyzed using a similar MMRM model as the one described for the primary endpoints; except for the analysis of the endpoint of FPG, the baseline FPG will replace the baseline 24-hour mean weighted glucose as one of the fixed effects.

The change in HbA1c from baseline (Day 1) to Day 6 of Week 10 (Day 70) will be analyzed using an analysis of covariance (ANCOVA) model with treatment as a factor and baseline HbA1c as a covariate.

In order to control the family-wise Type I error, a sequential testing procedure will be implemented. In the hierarchical testing order, the primary endpoints of 24-hour mean weighted glucose at Week 10 will be tested first, followed by 24-hour mean weighted glucose at Week 4, then the secondary endpoints: FPG at Week 10, 4-hour mean weighted glucose at Week 10, then FPG at Week 4, and 4-hour mean weighted glucose at Week 4.

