8.5.3 Analysis of the exploratory variable(s)

The MAGE will be calculated for each patient by taking the arithmetic mean of blood glucose increases or decreases (from blood glucose nadirs to peaks or vice versa) when both ascending and descending segments exceed the value of 1 SD of the blood glucose concentration in a 24 hour period. The proportion of time that patients had plasma glucose measurements <70 mg/dL, ≥ 70 mg/dL and ≤ 180 mg/dL, and >180 mg/dL will be calculated as the time period the glucose level falls into the pre-specified criteria, divided by the total time period. Detailed calculation will be described in the SAP.

Tertiary endpoints will be analyzed using a similar MMRM model to the primary and secondary endpoints, with the baseline value of the dependent variable included as a fixed effect factor.

Daily 24-hour glucose profile collected during the 1 week lead-in period and during Week 10 will be summarized descriptively and plotted. The difference and/or similarity will be discussed.

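### The protocol points to two models for Week 10 HbA1c, and the ANCOVA in 8.5.2, as written, uses only Day 70 values

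*Protocol*

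**What the plan says.** - **Objective (Protocol 2.2).** HbA1c is a secondary objective at two time points: "To compare the effect on HbA1c levels and 2-hour PPG after 4 and 10 weeks of dosing".
- **Endpoint lists (8.4.2, 8.4.3).** HbA1c is not among the secondary endpoints. It appears as exploratory: "Change from baseline (Day 1) to Week 10 (Day 70) and Week 4 (Day 28) in HbA1c".
- **Named model (8.5.2, repeated in the synopsis).** "The change in HbA1c from baseline (Day 1) to Day 6 of Week 10 (Day 70) will be analyzed" by an "analysis of covariance (ANCOVA) model with treatment as a factor and baseline HbA1c as a covariate". Week 4 is not mentioned.
- **Exploratory analysis (8.5.3).** "Tertiary endpoints will be analyzed using a similar MMRM model to the primary and secondary endpoints", with the baseline of the dependent variable as a fixed effect. The protocol defines no tertiary tier.
- **Sampling (5.1.2.4, Table 2).** Central-laboratory "HbA1c at Screening, Randomization (Day 1), Day 15, Day 22, Day 57, Day 64, Day 70, and ET". No HbA1c sample is scheduled on Day 28.
- **Other endpoints (8.5.1, 8.5.2).** The primary endpoint, FPG and 2-hour mean weighted PPG are analysed by MMRM. For the primary, "All post-baseline measurements (including early termination visits) of the 24-hour mean weighted glucose will be included in the analysis".

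**The concern.** One outcome has two candidate analyses and no stated order of precedence. The two can give different Week 10 estimates, and nothing in the protocol says which is the reported result. Settling this after unblinding would leave a choice between two known answers.

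The model that names HbA1c is also the weaker of the two on the protocol's own terms. It is tied to a single visit, although five post-baseline draws and an early termination draw are scheduled. The protocol uses a likelihood-based repeated-measures model for the primary, FPG and PPG endpoints. Its interim analysis (8.5.4) includes patients with only a Week 4 visit in order to gain precision at Week 10. No reason is given for treating HbA1c differently.

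At stake are the precision of the Week 10 HbA1c estimate, its robustness to dropout, and a clear source for the Week 4 comparison named in 2.2.

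**Working it through.** **1. The texts side by side**

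| Section | Tier of HbA1c | Time points | Model |
|---|---|---|---|
| 2.2 | Secondary objective | Weeks 4 and 10 | none given |
| 8.4.2 | Not listed | none | none |
| 8.4.3 | Exploratory | Week 4 (Day 28), Week 10 (Day 70) | none given |
| 8.5.2, synopsis | Under secondary variables | Day 70 only | ANCOVA |
| 8.5.3 | Tertiary (undefined), under exploratory variables | not restricted | MMRM |

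The natural reading of the tertiary tier is the 8.4.3 list, since 8.5.3 is headed for the exploratory variables. That list includes HbA1c. On this reading Week 10 HbA1c has two models, and Week 4 has one through a sentence that does not name HbA1c.

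**2. The plan's own figures**

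Section 8.2 gives no power for HbA1c. Its stated powers do reproduce with 39 per arm and a two-sided t-test at 0.05:

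- 24-hour glucose, 18 mg/dL with SD 24: 0.905 (stated 90%).
- FPG, 30 mg/dL with SD 45: 0.828 (stated about 83%).
- 24-hour glucose, 32 mg/dL with SD 50: 0.797 (stated about 80%).

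Dropout: 55 × 0.70 = 38.5, consistent with 39 completers. The remainder is 55 − 39 = 16 per arm, and 16/55 = 29%.

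**3. Precision of MMRM relative to an observed-case ANCOVA**

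Inputs: m = 39 patients per arm with a Day 70 value (8.2). n is the number with any post-baseline HbA1c: 55 if all 16 dropouts have an earlier value, 39 + 8 = 47 if half do. ρ is the correlation between earlier and Day 70 HbA1c change. The protocol gives no HbA1c SD or correlation, so ρ = 0.5 to 0.9 is an assumption.

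With one earlier value, monotone missingness and random dropout, the variance ratio (MMRM to ANCOVA) is 1 − (1 − m/n)ρ².

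| ρ | Dropouts with an earlier value | Variance ratio | Equivalent n per arm (39 / ratio) | ANCOVA SE larger by |
|---|---|---|---|---|
| 0.5 | half | 1 − (8/47)(0.25) = 0.957 | 40.7 | 2% |
| 0.5 | all | 1 − (16/55)(0.25) = 0.927 | 42.1 | 4% |
| 0.9 | half | 1 − (8/47)(0.81) = 0.862 | 45.2 | 8% |
| 0.9 | all | 1 − (16/55)(0.81) = 0.764 | 51.0 | 14% |

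The variance falls by about 4 to 24%. Since √0.957 = 0.978 and √0.764 = 0.874, the MMRM standard error is about 2 to 13% smaller. The gain equals roughly 2 to 12 patients per arm.

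**4. Direction of bias**

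An illustrative simulation assumed all its inputs: true difference −0.80, SD 0.8, about 34% dropout driven by poor early response, ρ = 0.5 to 0.9. The observed-case difference (without baseline adjustment) averaged −0.74 to −0.69, and the likelihood-based one −0.80. This shows the direction only. Under completely random dropout neither analysis is biased.

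**5. The Week 4 date**

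Section 8.4.3 places Week 4 HbA1c on Day 28. Table 2 and 5.1.2.4 schedule the Week 4 draw on Day 22, with none on Day 28.

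**The case against.** **The conflict is inferred.** Section 8.5.3 does not name HbA1c, whereas 8.5.2 names outcome, visit, model and covariate. A specific-over-general reading (ANCOVA for Week 10, MMRM for the rest) would remove the clash. That reading is possible, but the protocol does not state it, and it would split one endpoint across two models by visit. The ambiguity stands.

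**Week 4 is not left without an analysis.** A reader of 8.5.2 alone might infer that it is. If 8.5.3 covers HbA1c, it supplies the Week 4 comparison, so the protocol is inconsistent rather than silent.

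**The ANCOVA need not be complete-case.** Section 8.3.1 applies the modified ITT set to all efficacy analyses, an early termination HbA1c is drawn, and the SAP could carry it forward or impute. This is fair: the loss of 16 per arm holds only for the text as written. A SAP rule would still inherit a protocol that points to two models.

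**Bias is not shown.** A reader might infer that the Week 10 effect will be attenuated by a known amount. Section 8.2 ties its extra dropout allowance to study length and visit burden, not glycemia. Section 3.9.1 does discontinue patients with a confirmed FPG of 270 mg/dL or more, so some loss can follow glycemia, but nothing says how much. That rule also acts on FPG, which an HbA1c MMRM captures only so far as it is reflected in observed HbA1c.

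**Materiality is limited.** A baseline-adjusted ANCOVA at the final visit is a standard analysis. HbA1c is outside the testing hierarchy and the power calculation. Both points stand.

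**Conclusion.** The point holds as an inconsistency with a worthwhile improvement attached. The protocol points to two models for Week 10 HbA1c and reaches Week 4 only through an undefined tier. The model named in 8.5.2 does not, as written, use HbA1c values already scheduled.

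The precision gain from an MMRM is a variance reduction of about 4 to 24%. It rests on the 30% dropout in 8.2, an assumed correlation of 0.5 to 0.9, half to all of the dropouts having an earlier value, and no missing-data rule in the SAP. The upper end needs both a high correlation and an earlier value from every dropout, so it should not be read as the expected gain. The MMRM also protects against bias when dropout depends on observed HbA1c, but the documents give no basis for sizing that bias.

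No inference should be drawn about the primary result. HbA1c is not in the hierarchical order, and the primary conclusion and Type I error control are unaffected.

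**What to change.** Amend the protocol in the synopsis, 8.4.3, 8.5.2 and 8.5.3:

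1. Name one primary HbA1c model: an MMRM over all scheduled post-baseline visits (Days 15, 22, 57, 64 and 70), with treatment, visit, treatment-by-visit and continuous baseline HbA1c. Report the Week 4 and Week 10 contrasts.
2. Drop the HbA1c stratum term (below 8.5% versus 8.5% or above) from this model. It is a coarse duplicate of the continuous baseline, and 3.5 describes blocking by site without HbA1c stratification.
3. Keep the Day 70 ANCOVA as a sensitivity analysis, with its handling of missing Day 70 values stated.
4. Define the tertiary tier or replace the word, and state one tier for HbA1c that agrees with 2.2 and 8.4.2.
5. Reconcile the Week 4 HbA1c date: Day 28 in 8.4.3 against a Day 22 draw in Table 2 and 5.1.2.4.

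The cost is a small protocol text change, matching SAP wording and slightly more modelling. If Week 4 is reconciled to the existing draw, no new samples, visits or patients are needed.

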Note: Entry into the lead-in period (Day -28) should occur at least 7 days after Screening but no later than 14 days after receiving the Screening laboratory results. Study visits during the lead-in period and the double-blind treatment period should occur on the designated visit day ± 3 days.

- Screening can be performed over multiple visits. Entry into the lead-in period should occur at least 7 days after Screening and no later than 14 days after screening.
- If the patient discontinues during one of the 7 day CGM periods, remove CGM device. The CGM device should not remain in place longer than 10 days.
- Standard safety blood tests, urinalysis for safety analysis, and HbA1c will be performed 30 minutes prior to the standardized breakfast meal.
- A complete physical examination will be performed on days designated with an X. A brief physical examination will be performed on days designated with an X^d. See Section 5.2.2 for details.

- e. If patient is discontinuing the study due to an adverse event, a 5 mL blood sample for assessment of exenatide plasma concentration will be collected.
- f. See [Table 4](#) for a list of the safety laboratory variables for this study. Patients who discontinue should have a standard safety laboratory panel collected at the conclusion of their participation.
- g. Women of childbearing potential only.
- h. Glucose levels will be drawn 30 minutes before and just prior to breakfast and 30, 60, 120, and 180 minutes after breakfast. The post meal glucose tolerance test is provided in a 3 day window.
- i. Patients must be fasting at this time point.
- j. Includes hepatitis screen panel (anti-hepatitis C virus and HBsAg only).
- k. Patients should be instructed to perform fasting SBGM daily, and instructed to call the site if they have a FPG ≥ 270 mg/dL (15 mmol/L) for 3 consecutive days. The patient should have a FPG by central laboratory; if ≥ 270 mg/dL (15 mmol/L), the patient should be discontinued. If the patient has not performed fasting SBGM and the central laboratory FPG at Day -7 ≥ 270 mg/dL (15 mmol/L), the patient should be considered for discontinuation.

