5.1.2 Secondary efficacy assessments

5.1.2.1 Postprandial glucose

Secondary assessments including the 2-hour mean weighted PPG and 2-hour PPG, (2 hours after the breakfast meal) will be obtained during blood draws for glucose measurements after the standardized breakfast during the onsite monitoring visits on Day -7, Day 22, and Day 64 (3 day window) and will be processed at the central laboratory. The 2-hour mean weighted PPG will be estimated by dividing the area under the 2-hour glucose curve by 2 hours. Detailed calculation will be defined in the SAP.

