5.3 Other assessments

5.3.1 Procedures before and after the standardized breakfast meal

- The time of commencement of the breakfast meal on the day of the visit will be considered the 0 time point for all testing. Note: There is a window of ± 2 minutes for sampling time points.
- At 60 minutes prior to the breakfast meal, confirm CGM system device is functioning properly.

- At 30 minutes prior to the breakfast meal, obtain blood specimens for glucose and standard safety assessments. Have the patient void urine (use this specimen for the urinalysis for the standard safety labs).
- On Day 22 and Day 64, perform PK blood sampling and biomarker analysis (prior to the breakfast meal).
- The time T1 = -30 will mark the beginning of the 24-hour blood glucose collection.
- Just prior to the breakfast meal, obtain blood specimens for glucose, insulin, glucagon, and C-peptide.
- The patient should consume the entire meal within 30 minutes. Note the time the meal was started and completed. Record on the eCRF.
- Obtain blood specimens for glucose, insulin, and c-peptide at 30, 60, 120, and 180 minutes following the breakfast meal.

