8.4.2 Secondary endpoints

The secondary endpoints for this study are the following:

- Change in 24-hour mean weighted glucose between Day 1 of Week 10 (Day 64/65) and Day 6 of Week 10 (Day 69/70) within each EQW-treated patient
 - Note that Day 6 data will consist of data from Day 6 \pm 1 day (Days 5 through 7)
 - There will also be an average of change in 24-hour mean weighted glucose from baseline to Days 1 to 6 of Week 10 and Week 4 calculated (SD, MAGE, “Distance travel”, “Energy”)
- Change from baseline (Day 1) to Day 6 of Week 10 (Day 70) and Day 6 of Week 4 (Day 28) in FPG
- Change from baseline (Day -1) to Day 6 of Week 10 (Day 69) and Day 6 of Week 4 (Day 27) in 2-hour mean weighted PPG (after the breakfast meal)

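### The alpha-controlled testing order names a 4-hour mean weighted glucose that the protocol never defines, and leaves out the listed secondary endpoint, 2-hour mean weighted PPG

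*Protocol*

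**What the plan says.** **The order.** Section 8.5.2 puts the two primary comparisons of 24-hour glucose first, Week 10 before Week 4. Its four remaining steps read: "FPG at Week 10, 4-hour mean weighted glucose at Week 10, then FPG at Week 4, and 4-hour mean weighted glucose at Week 4". The synopsis gives the same order.

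**The listed meal endpoint.** Section 8.4.2 lists change from baseline "in 2-hour mean weighted PPG (after the breakfast meal") at Weeks 10 and 4. Section 5.1.2.1 derives it from central-laboratory samples: "The 2-hour mean weighted PPG will be estimated by dividing the area under the 2-hour glucose curve by 2 hours". In Section 8.5.2 this endpoint and FPG "will be analyzed using a similar MMRM model as the one described for the primary endpoints".

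**The meal test.** Section 5.3.1: "Obtain blood specimens for glucose, insulin, and c-peptide at 30, 60, 120, and 180 minutes following the breakfast meal". The study plan notes in Section 4 agree: "Glucose levels will be drawn 30 minutes before and just prior to breakfast and 30, 60, 120, and 180 minutes after breakfast".

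**The error claim.** Section 8.2 says family-wise error is held at 0.05 for primary and secondary endpoints by sequential testing and refers to Section 8.5.2 for the order. Section 8.5.1 makes the same claim.

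**Which endpoints are secondary.** Section 2.2 has as a secondary objective "To compare the effect on HbA1c levels and 2-hour PPG after 4 and 10 weeks of dosing". Section 8.4.3 has as an exploratory endpoint "Change from baseline (Day 1) to Week 10 (Day 70) and Week 4 (Day 28) in HbA1c".

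**The concern.** A fixed sequence protects the error rate only if every hypothesis in it is identified before the data are seen. Here the variable at steps 4 and 6 has a name and nothing else: no source, start time or endpoint entry. The meal endpoint that the protocol does define is missing from the order.

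Two things are at stake. A significant result for 2-hour mean weighted PPG would carry no family-wise protection, although the protocol says secondary endpoints have it. And passage from step 4 to step 5 (FPG at Week 4) depends on a test that analysts would have to specify themselves. If they did so after unblinding, the confirmatory hypothesis would be a post-hoc choice.

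**Working it through.** **1. The plan's own power figures (Section 8.2).** With n = 39 per arm and two-sided alpha 0.05, the normal approximation is power = Φ(δ / (SD·√(2/n)) − 1.96), with √(2/39) = 0.2265.

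| Statement in 8.2 | δ / SD (mg/dL) | Stated | Normal | Noncentral t, 76 df |
|---|---|---|---|---|
| 24-hour glucose, Week 4 | 18 / 24 | 90% | 0.912 | 0.905 |
| FPG | 30 / 45 | about 83% | 0.837 | 0.828 |
| Third statement, labelled 24-hour glucose | 32 / 50 | about 80% | 0.807 | 0.797 |

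All three reproduce, and none refers to a 4-hour variable. The third uses SD 50 for a measure given SD 24 earlier in the same paragraph. It may be a mislabelled statement for the meal endpoint, but that is inference only.

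**2. The six steps against the endpoint lists.**

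| Step | Variable in the order | Defined in |
|---|---|---|
| 1 | 24-hour glucose, Week 10 | 8.4.1 |
| 2 | 24-hour glucose, Week 4 | 8.4.1 |
| 3 | FPG, Week 10 | 8.4.2 |
| 4 | 4-hour glucose, Week 10 | nowhere |
| 5 | FPG, Week 4 | 8.4.2 |
| 6 | 4-hour glucose, Week 4 | nowhere |

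Undefined: 2 of 6. Dependent on an undefined step: steps 4, 5 and 6, which is 3 of the 4 secondary steps.

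**3. What the four secondary places should hold.** Section 8.4.2 lists the intra-patient Day 1 to Day 6 comparison, FPG and 2-hour mean weighted PPG. Section 8.5.2 makes the first descriptive only. Two endpoints at two weeks give 2 × 2 = 4 tests. FPG takes two places, and the 4-hour variable occupies the two that 2-hour mean weighted PPG would fill.

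**4. Data available for a 4-hour mean.** The last laboratory sample is at 180 minutes, so a 4-hour post-meal area lacks 240 − 180 = 60 minutes. Counting from the −30 minute sample, coverage is 30 + 180 = 210 minutes, or 3.5 hours. CGM records about every 5 minutes (Section 5.2.6.2), so a 4-hour window would hold about 240 / 5 = 48 readings. The protocol does not say which window.

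**5. Size of the gap in error control.** Assume that the two PPG P values (Weeks 10 and 4) were each read at 0.05 as confirmatory, outside the order. The family-wise rate is then bounded by 0.05 + 2 × 0.05 = 0.15 rather than 0.05. This is an upper bound. The true figure depends on correlations that the protocol does not give.

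**6. Days.** Section 8.4.2 dates the PPG endpoint to Days -1, 27 and 69. The meal tests are on Days -7, 22 and 64, with a 3-day window (Section 5.1.2.1). Days 22 and 64 are the first days of Weeks 4 and 10, not Day 6.

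**The case against.** **A reader might infer that 2-hour mean weighted PPG is never tested.** The protocol does not support that. Section 8.5.2 gives it an MMRM like the primary one, and Section 8.5.1 says that model yields P values. What it lacks is a protected place in the order.

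**A reader might infer that the 4-hour variable cannot be computed.** That holds only for the laboratory meal test. The order speaks of mean weighted glucose, the wording used for the CGM measure, whereas the laboratory measure is called mean weighted PPG. A 4-hour mean could be cut from CGM data. This part of the objection stands: the defect is that the variable is undefined, not that it is infeasible.

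**The harm is limited.** The primary tests and Week 10 FPG come first, and Section 8.1 keeps analysis personnel blinded until database lock, so post-hoc substitution is a possibility, not a prediction. This also stands, but blinding does not supply the missing definition.

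**The analysis plan could settle it.** The protocol leaves detailed calculations to the SAP. It does not leave open which endpoints are tested or in what order; it fixes both here. An SAP that used the 2-hour endpoint would contradict the protocol, and one that kept the 4-hour wording would inherit the gap.

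**Conclusion.** The testing order is wrong as written. Steps 4 and 6 have no defined variable, steps 4 to 6 cannot be executed unambiguously, and the claimed Type I error control does not extend to 2-hour mean weighted PPG. Steps 1 to 3 stand, as do the stated power figures.

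That the 4-hour wording is a slip for the 2-hour endpoint is likely from the count of places, but the protocol does not establish it. The conclusion does not depend on it.

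A reader might go further and say the error claim is also false for HbA1c, MAGE and time in range. It is so only if Section 2.2 defines the family. The endpoint list in Section 8.4.2 excludes them and Section 8.4.3 calls them exploratory. This is a separate and lesser inconsistency.

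**What to change.** Before unblinding:

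1. In the synopsis and Section 8.5.2, replace both 4-hour entries with 2-hour mean weighted PPG. If a 4-hour variable was truly intended, define it with its data source and start time, list it in Section 8.4.2, and give 2-hour mean weighted PPG its own place in the order.
2. Reconcile the PPG endpoint days (Days -1, 27 and 69) with the meal-test days (Days -7, 22 and 64) wherever the endpoint appears. Otherwise the substituted endpoint is dated to days without a meal test.
3. As a secondary edit, align Section 2.2 and its synopsis copy with Sections 8.4.2 and 8.4.3 on whether HbA1c, MAGE, time in range and 2-hour PPG (the single value) are secondary or exploratory. Correct the HbA1c row, whose outcome measure is the PPG text. The protected family is then defined once.
4. Check whether the third power statement in Section 8.2 belongs to the meal endpoint, and label it accordingly.

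The cost is a wording amendment. If the 2-hour endpoint is used, no visit, sample or patient is added.
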